9.3 Area of Pain

The scar pain area reported by the subject will be mapped and drawn on the skin with a skin marker pen.

The longitudinal axis of the painful area and the total painful area will be measured. The boundary of the spontaneous pain felt by the subject as well as the sites for injection at 2-cm intervals and starting 1 cm from the edge of the longitudinal axis of the pain area will be marked as represented in [Figure 3](#) in Section [6.1.5](#). A photograph will be recorded with a ruler for scale and used to reproduce the administration scheme on injection test 1, injection test 2 and IMP dosing on Day 1.

10 EXPLORATORY ASSESSMENTS

The following exploratory assessments will be performed during the study at specific timepoints as described in the study schedule of assessments in Section 18.1.

10.1 Quality of Life questionnaire Short Form-36

The SF-36 is a 36-item, subject-reported survey of subject health. The SF-36 consists of eight scaled scores (vitality, physical functioning, bodily pain, general health perceptions, physical role functioning, emotional role functioning, social role functioning and mental health). The higher the score the less disability.

10.2 Rescue Medication

Details on the rescue medication are provided in Section 6.2.

Subjects will be provided with a rescue diary (paper) to record each rescue medication intake, dose, each pain increase (AE), start and stop date and time and current NRS score just before the rescue medication is taken.

If rescue medication is taken, an AE and the corresponding rescue medication should be recorded in the eCRF.

11 STATISTICAL ANALYSES

11.1 Analyses Populations

The following populations will be used for statistical analyses:

- Screened population: All subjects screened (i.e. who signed the informed consent),
- Run-in population: All subjects who received at least one injection in the pre-randomisation run-in period (Part A),
- Randomised population: All subjects randomised in the double-blind period (Part B),
- Safety population: All subjects who received at least one dose of the study drug during the randomised double-blind period (Part B),
- Per protocol (PP) population: All subjects from the randomised population for whom no major protocol deviation occurred.

11.2 Sample Size Calculation

No prospective calculations of statistical power is made.

An appropriate sample size cannot be determined statistically as no previous human data from previous clinical trials are available. A sample size of six subjects per dose of Dysport has been selected. Approximately 24 subjects will be randomised in the double-blind period. Subjects who withdraw within the six first weeks from dosing will be replaced.

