	
 Safety assessments (physical examination, vital signs measurements, collection of adverse events (AEs) and recording of concomitant medication). 
Subjects will be dosed if considered as consistent in pain perception from the screening visit (i.e. variability < 2 for the average spontaneous NRS score pre-injection tests in Part A, pre-QST and pre-dosing, and clinically plausible as per investigator's judgement).
 
Subjects will then be assessed for pharmacodynamics and safety for up to 16 weeks post-dose.
 
Subjects will be discharged from the study after safety assessments (physical examination, vital signs) during an end of study (EoS) visit.

Planned number of subjects	
Approximately 24 subjects are expected to be randomised in Part B into four arms, each with six subjects treated with either one dose of Dysport or placebo.
 
Subjects who withdraw within the first six weeks after investigational medicinal product (IMP) dosing will be replaced. Replacement subjects will receive the same schedule and treatment as the subject they have replaced.
 
Approximately 60 subjects are expected to enter the Part A to reach the targeted randomised subject number in Part B.

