Statistical methodology	This is an exploratory study to assess how Dysport might be of benefit in chronic pain. An appropriate sample size cannot be determined statistically as insufficient human data are available from previous clinical trials. Approximately 24 subjects (six subjects per treatment arm) will be randomised in the double-blind period (Part B). Subjects who withdraw within the first six weeks after IMP dosing for reasons other than lack of efficacy will be replaced. Only descriptive statistics will be provided.

TABLE OF CONTENTS

RATIONALE FOR PROTOCOL AMENDMENT # 2	12
LIST OF DEFINITIONS AND ABBREVIATIONS.....	15
1 BACKGROUND INFORMATION	18
1.1 Introduction.....	18
1.2 Name and Description of the Investigational Medicinal Product	19
1.3 Non-Clinical Data	19
1.4 Clinical Data.....	20
1.5 Rationale for the Study.....	20
1.6 Dosage Selection	20
1.7 Population to be Studied	21
1.8 Known and Potential Risks to Human Subjects	21
2 STUDY OBJECTIVES.....	23
2.1 Primary Objective.....	23
2.2 Secondary Objectives	23
2.3 Exploratory Objectives.....	23
3 INVESTIGATIONAL PLAN	24
3.1 Overall Study Design and Plan.....	24
3.2 Study Endpoints.....	25
3.2.1 Primary Endpoints	25
3.2.2 Secondary Endpoints	25
3.2.3 Exploratory Endpoints.....	25
3.3 Study Duration.....	25
3.4 Randomisation and Blinding	26
3.4.1 Method of Randomisation	26
3.4.1.1 Pre-randomisation Run-in Period (Part A)	26
3.4.1.2 Randomised Double-blind Period (Part B)	26
3.4.2 Blinding.....	27
3.4.3 Code-break	27
3.5 Stopping Rules and Discontinuation Criteria	28
3.6 Source Data Recorded on the Case Report Form.....	28
4 SELECTION AND WITHDRAWAL OF SUBJECTS	29
4.1 Inclusion Criteria	29
4.2 Exclusion Criteria	29
4.3 Rationale for Specific Inclusion / Exclusion Criteria	30
4.4 Withdrawal of Subjects	31
5 STUDY CONDUCT.....	32
5.1 Study Schedule of Assessments.....	32
5.2 Study Visits and Procedures	32
5.2.1 Screening.....	32

5.2.1.1	Informed Consent	32
5.2.1.1	Screening Procedures	32
5.2.2	Pre-randomisation Run-in Period (Part A)	32
5.2.3	Randomised Double-blind Period (Part B)	33
5.2.3.1	Baseline visit	33
5.2.3.2	Randomised Period	33
5.2.4	Early Discontinuation or End of Study Visit	34
5.3	Lifestyle Restrictions	34
5.3.1	Diet	34
5.3.2	Alcohol	34
5.3.3	Physical Activity	34
5.3.4	Prohibited Concomitant Medications and non Drugs Therapies	34
5.4	Priority Order on Study Procedures	35
6	TREATMENT OF SUBJECTS	36

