3.4.1.2 Randomised Double-blind Period (Part B)

Subjects will be randomised to receive Dysport 2.5 U, Dysport 2.5 U placebo, Dysport 10 U, Dysport 10 U placebo, Dysport 20 U, Dysport 20 U placebo with a ratio 3:1:3:1:3:1 (blocks of 12 subjects).

Following confirmation of eligibility after injection test 2, subjects will be assigned to a randomisation number and allocated to one of the treatment groups in a chronological order, i.e. first eligible subject will be given the first randomisation number as detailed in [Table 2](#).

Table 2 Part B Randomisation Numbers

Part B Randomisation Numbers	Part B Replacement Randomisation Numbers
From CCI [REDACTED]	From CCI [REDACTED]

Mirror lists of randomisation numbers will also be produced to allow the randomisation of replacement subjects (e.g. the subjects who withdraw within six first weeks after IMP dosing) or to be used for the replacement of kits which could be damaged during the IMP reconstitution. For example, number CCI [REDACTED] will be used to randomise the replacement for the subject who was randomised with number CCI [REDACTED].

The sponsor's randomisation manager will prepare and keep the master lists of pre-randomisation run-in numbers and randomisation numbers. A copy of these lists will be sent confidentially to:

- Pharmaceutical Development Clinical Supply Chain
Beaufour Ipsen Industrie SAS
[name]
[name].

The lists and their copies will be kept confidential in secure locations. Access to the randomisation lists will be restricted until authorisation is given to release them for final analysis.

An identification code assigned to each subject will be used in lieu of the subject's name to protect the subject's identity when reporting AEs and/or other study-related data.

3.4.2 *Blinding*

Only the pharmacist or delegate in charge of drug preparation at the clinical research unit (CRU) and the monitor responsible for pharmacy monitoring will be partially unblinded. These personnel will be fully trained on the importance of their role in maintaining the blind for the subject, the investigator and the remainder of the study team. The unblinded staff at the CRU will not carry out any study assessments other than those they are assigned to.

All other staff at the CRU, the sponsor and the subjects will be blinded to treatment allocations during the study.

3.4.3 *Code-break*

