4.4 Withdrawal of Subjects

In accordance with the declaration of Helsinki and International Council for Harmonisation (ICH) GCP, each subject is free to withdraw from the study at any time, for any reason (e.g. withdrawal of consent, AE).

The investigator can withdraw a subject from the study at any time for any reason (e.g. protocol deviation, non compliance with the protocol conditions, lack of cooperation, in the event of concurrent illness, AE, or other reasons concerning the health or well-being of the subject).

The reason for and date of withdrawal from the study must be recorded in the eCRF.

If withdrawal is based on subject's decision every attempt will be made to determine:

- The reason for withdrawal,
- Whether the subject also decides to withdraw his/her consent for the sponsor to collect and use the data collected up to the withdrawal point.

Data collected prior to subject withdrawal may be kept in study records and shared for further analyses unless the subject formally specifies his/her decision to withdraw consent for using data already collected.

Should a subject be withdrawn from the study after IMP dosing and before normal study completion, all efforts will be made to complete the EoS assessments and report the observations up to the time of withdrawal as thoroughly as possible. A complete final evaluation at the time of the subject's withdrawal should be made whenever possible.

Subjects who withdraw within the first six weeks after IMP dosing for reasons other than lack of efficacy will be replaced. Replacement subjects will receive the same schedule and treatment as the subject they have replaced.

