2.4.2 Randomised Double-Blind Period (Part B)

Subjects will be randomised to receive Dysport 2.5 U, Dysport 2.5 U placebo, Dysport 10 U, Dysport 10 U placebo, Dysport 20 U, Dysport 20 U placebo with a ratio 3:1:3:1:3:1 (blocks of 12 subjects).

Following confirmation of eligibility after injection test 2, subjects will be assigned to a randomisation number and allocated to one of the treatment groups in a chronological order, i.e. first eligible subject will be given the first randomisation number.

Mirror lists of randomisation numbers will also be produced to allow the randomisation of replacement subjects (e.g. the subjects who withdraw within six first weeks after Investigational Medicinal Product (IMP) dosing) or to be used for the replacement of kits which could be damaged during the IMP reconstitution. For example, number CCI will be used to randomise the replacement for the subject who was randomised with number CCI.

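### The protocol and SAP give two different rules on whether a subject who withdraws within six weeks for lack of efficacy is replaced; one of them lets an arm's size grow with its own treatment failures

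*Protocol*

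**What the plan says.** Two rules stand side by side in current text.

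**With the exception.** Protocol 4.4 says: "Subjects who withdraw within the first six weeks after IMP dosing for reasons other than lack of efficacy will be replaced". The synopsis row on statistical methodology has the same restriction: "for reasons other than lack of efficacy will be replaced".

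**Without the exception.** The synopsis row on the planned number of subjects says: "Subjects who withdraw within the first six weeks after investigational medicinal product (IMP) dosing will be replaced". Protocol 11.2 says: "Subjects who withdraw within the six first weeks from dosing will be replaced". SAP 2.3 repeats the 11.2 sentence.

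**Examples that also omit it.** Protocol 3.4.1.2 explains the mirror randomisation lists by the example of "the subjects who withdraw within six first weeks after IMP dosing". SAP 2.4.2 has the same example: "the subjects who withdraw within six first weeks after Investigational Medicinal Product (IMP) dosing".

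The synopsis planned-numbers row and 4.4 both add: "Replacement subjects will receive the same schedule and treatment as the subject they have replaced". SAP 2.6, which records changes from the protocol's statistical section, does not mention replacement.

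**The concern.** Leaving for lack of efficacy is an outcome of treatment. If such subjects are replaced in the same arm, the arm with more failures gains more subjects, and each failure counts for less in that arm's percentages and means. The exception in 4.4 prevents this; the text in 11.2 and SAP 2.3 does not.

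The case is foreseeable. Protocol 6.2 has the investigator consider discontinuing a subject whose scar pain stays uncontrolled after three days at the maximum rescue dose. If that happens before Week 6, the two rules give opposite answers.

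A replacement also has a recruitment cost. The synopsis expects about 60 subjects in Part A to randomise about 24, or 60/24 = 2.5 entrants for each subject randomised.

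**Working it through.** **Planned size.** Protocol 11.2: "A sample size of six subjects per dose of Dysport has been selected", with about 24 in total. The 3:1:3:1:3:1 ratio in 3.4.1.2 sums to a block of 12. Two blocks give 3 × 2 = 6 per Dysport dose and 3 × (1 × 2) = 6 pooled placebo, so 4 × 6 = 24. The plan's figure reproduces.

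**How subjects are counted.** The primary analysis uses the randomised population (SAP 5.7.3.1), which is everyone randomised in Part B (SAP 4.3). A withdrawn subject and the replacement are therefore both in it. With k lack-of-efficacy withdrawals in an arm of six:

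- not replaced: weight of failures = k/6
- replaced, and no replacement fails: weight = k/(6 + k)

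| k | Not replaced | Replaced | Difference |
|---|---|---|---|
| 1 | 1/6 = 16.7% | 1/7 = 14.3% | 2.4 points |
| 2 | 2/6 = 33.3% | 2/8 = 25.0% | 8.3 points |

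**Letting replacements fail too.** The documents give no rate, so assume that each subject, replacement or not, fails early with probability p. Without replacement the expected share of failures is p. With k ~ Binomial(6, p) and one replacement per failure, it is (1 + p) × E[k/(6 + k)]. If replacement continues until six stay, k is negative binomial and the expected share is E[k/(6 + k)].

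| Assumed p | No replacement | One replacement each | Replaced until six stay |
|---|---|---|---|
| 10% | 10% | 8.9% | 8.7% |
| 20% | 20% | 18.2% | 17.6% |

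The expected shift is 1.1 to 1.3 points at p = 10% and 1.8 to 2.4 points at p = 20%.

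**How often it would arise.** The chance of at least one such withdrawal in an arm of six is 1 − (1 − p)^6: 47% at p = 10% and 74% at p = 20%. The chance of two or more is 11% and 34%.

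**By-timepoint summaries.** SAP 5.7.3.2 applies no missing-data handling to the primary endpoints, and SAP 5.7.4 specifies none for change from baseline by timepoint. SAP 6.2 moves a withdrawal assessment to the next empty visit; beyond that, a leaver has no observed value. Later summaries rest on the remaining subjects plus any replacements. In the k = 2 example with both replacements staying, that is six observed values under one rule and four under the other.

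**The case against.** The strongest answer is that the conflict is one missing phrase with small consequences. Much of this stands.

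- **Attrition is reported.** A reader might infer that replacement hides the failures. The SAP does not support that. SAP 5.2 tabulates withdrawals and their reasons by treatment group. SAP 5.7.3.2 lists subjects with missing primary endpoints, with the reason for and timing of discontinuation. SAP 5.1.2 displays missing data, and SAP 5.7.4.2 puts group sizes on the mean-change graph. In the k = 2 example the randomised arm is 8, so six observed values would appear with two missing.
- **33.3% against 25.0% is not the expected effect.** It requires two failures in one arm and replacements that all stay. Allowing replacements to fail brings the expected shift down to 1 to 2.4 points.
- **Nothing inferential depends on it.** Protocol 11.2 makes no power calculation, and SAP 5.7.1.1 plans no significance test.
- **The mirror-list passages are weaker evidence.** They describe a supply mechanism through an example and need not be read as separate replacement rules.
- **Further safeguards are largely in place.** Replaced subjects already stay in the randomised and safety populations (Protocol 11.1; SAP 4.3 and 4.4). Outside pharmacy preparation and pharmacy monitoring, site staff, the sponsor and subjects are blinded (Protocol 3.4.2).

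None of this settles which rule governs. Five statements of the rule split two against three, the synopsis contradicts itself, and SAP 2.6 does not resolve it.

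**Conclusion.** The contradiction is real and should be resolved. Under the no-exception text, arm size depends on outcome and treatment failures are diluted, not removed. The size is modest: 2.4 points of weight for one failure in an arm and 8.3 for two, if no replacement fails, or about 1 to 2.4 points in expectation if replacements fail at the same assumed rate of 10% to 20%. These rates are assumptions, because the documents give none. The planned 24 is unchanged. The remaining effect on reporting is limited to efficacy summaries at timepoints after withdrawal, where replacements supply values that the failures cannot.

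**What to change.** Adopt the rule already in 4.4 throughout. Add its exception for lack of efficacy to the synopsis planned-numbers row, Protocol 11.2 and SAP 2.3, and align the mirror-list examples in Protocol 3.4.1.2 and SAP 2.4.2. No new population definition, blinding statement or disposition table is needed.

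The cost is wording in five places. The downside is that an arm with lack-of-efficacy withdrawals may have fewer than six subjects followed to Week 16, which 4.4 already accepts.

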11.3 Statistical Methods

A SAP describing the planned statistical analysis in detail with tables, figures, and listings (TFLs) templates will be developed as a stand-alone document.

An overview of the main analysis strategy is provided in the following sections.

TFLs will be presented by treatment group (placebo, Dysport 2.5, 10 and 20 U). Some tables will also be described by total dose received in the painful injection area and the total dose received in the painful area divided by the painful area. This will be fully detailed in the SAP.

11.3.1 Safety Evaluation

11.3.1.1 Pre-randomisation Run-in Period (Part A)

Only listings will be provided.

11.3.1.2 Randomised Double-blind Period (Part B)

Descriptive statistics will be calculated on the safety parameters. No formal statistical tests of safety parameters are planned.

All AEs will be coded according to the latest version of the Medical Dictionary for Regulatory Activities (MedDRA).

Treatment emergent AEs (TEAE) summaries will include the overall incidence (by system organ class and preferred term), events by maximum intensity, events by relationship to study drug, events leading to discontinuation of study drug, and SAEs.

Physical examination findings, vital signs, ECG recordings and clinical laboratory parameters will be summarised descriptively at each timepoint. Actual and change from baseline data will be calculated and summarised where data are available. The investigator's interpretation of 12-lead ECGs will be listed.

Concomitant medications will be coded by using the latest version of the World Health Organisation (WHO) drug dictionary and will be summarised with the number and percentage of subjects receiving concomitant medication by drug class and preferred drug name.

Demographic variables (age, height, weight and body mass index) and medical and surgical history will be summarised.

11.3.2 *Pharmacokinetic Evaluation*

Not applicable.

11.3.3 *Pharmacodynamic/ Efficacy Evaluation*

11.3.3.1 *Pre-Randomisation Run-in Period*

Only listing on NRS data will be provided.

11.3.3.2 *Randomised Double-blind Period*

Analysis of the primary endpoints

Four endpoints have been defined to meet the study primary objective. They are presented in [Table 3](#) with their associated estimate and estimand.

Table 3 Primary Objective - Analysis of Primary Endpoints

Objective	Assessments	Endpoints	Estimate of treatment effect	Estimand
To describe the pharmacodynamic analgesic profile of intradermal doses of Dysport in subjects with abdominal or thoracic chronic scar pain.	Worst pain and average pain within the last 12 hours as assessed by the spontaneous NRS score.	Time to onset, i.e. time to decrease from baseline of two points in the spontaneous NRS score.	The number (%) of subjects who reach the time to onset in each treatment group. The mean time to onset in each treatment group.	For each estimate, the associated estimand will be based on "treatment policy" strategy (i.e. regardless of the intake of rescue medication).
		Peak-effect, i. e. maximal decrease from baseline in the spontaneous NRS score.	The mean peak in each treatment group.	
		Time to peak-effect, i.e. time to reach the peak-effect.	The mean time to reach the peak-effect in each treatment group.	
		Duration of effect, i.e. duration between time to onset and last timepoint with change from baseline in the spontaneous NRS score is ≥ 2 points.	The mean duration of effect in each treatment group (for the subjects who reach the time to onset).	

Only descriptive statistics will be provided. No statistical test will be performed.

As described in the above table, the estimand will be based on "treatment policy" strategy, which is the estimate of the treatment effect regardless of whether the subject has an intercurrent event during the study.

The following potential intercurrent events will be considered:

- The short-term use of rescue medication,
- The change in use of rescue medication.

Supplementary and sensitivity analysis will be performed to take into account these intercurrent events and to handle missing data. These analysis will be detailed in the SAP.

Analysis of the secondary endpoints

Endpoints have been defined to meet the study secondary objectives. They are presented in [Table 4](#) with their associated estimate and estimand.

Table 4 Secondary Objectives - Analysis of Secondary Endpoints

Objective	Assessments	Endpoints	Estimate of treatment effect	Estimand
To compare the efficacy of intradermal doses of Dysport to placebo.	Spontaneous pain as assessed by the spontaneous NRS score.	Change from baseline in the spontaneous NRS score to each scheduled timepoint.	Difference between each Dysport doses and the placebo group, in the mean change from baseline in the spontaneous NRS score to each scheduled timepoint.	For each estimate, the associated estimand will be based on "treatment policy" strategy (i.e. regardless of the intake of rescue medication).
	Stimulus-evoked pain as assessed by the NRS score during QST.	Change from baseline in the stimulus-evoked NRS score to each scheduled timepoint.	Difference between each Dysport doses and the placebo group, in the mean change from baseline in the stimulus-evoked NRS score to each scheduled timepoint.	For each estimate, the associated estimand will be based on "treatment policy" strategy (i.e. regardless of the intake of rescue medication).
To assess the safety and tolerability of a range of intradermal doses of Dysport	Refer to Section 11.3.1 .			

Only descriptive statistics will be provided. No statistical test will be performed. Supplementary and sensitive analysis will be performed to take into account the intercurrent event and to handle missing data. These analysis will be detailed in the SAP.

Exploratory efficacy endpoints

Endpoints have been defined to meet the study exploratory objectives. They are presented in **Table 5** with their associated estimate and estimand.

Table 5 Exploratory Endpoints - Analysis of Exploratory Endpoints

Objective	Assessments	Endpoints	Estimate of treatment effect	Estimand
To explore improvement of QoL using SF-36 questionnaire.	QoL assessed by the SF-36.	Change from baseline in SF-36 scores at each scheduled timepoint (scores/domain that will be used will be described in the SAP).	Difference between each Dysport doses and the placebo group in the SF-36 scores at each scheduled timepoint.	For each estimate, the associated estimand will be based on "treatment policy" strategy (i.e. regardless of the intake of rescue medication).
To explore concomitant use of rescue medication (analgesia).	Use of rescue medication during the study.	
 - Amount of rescue medication taken during the study. - Time to first intake of rescue medication. 	
 - Difference between each Dysport doses and the placebo group, in amount of rescue medication intake during the randomised double-blind period. - Difference between each Dysport doses and the placebo group, in the time to first intake of rescue medication during the randomised double-blind period. 	

Only descriptive statistics will be provided. No statistical test will be performed.

